The 20-item Trait section of the Spielberger Stait-Trait Inventory (STAI) also will be presented to the patients to assess anxiety symptoms before treatment. However, to assess ongoing treatment response, participants will complete the 20-item State section of the STAI at weekly intervals throughout the duration of the 3-month intervention by a clinician who will be blinded to patients' treatment group status. The STAI will be used to evaluate the process of change and to assess at-risk patients (i.e., worsening anxiety) regularly and systematically. Suicidal potential also will be carefully assessed. Contact time will be documented and content limited (to avoid simulating psychotherapy, which would seriously confound data interpretation).

Importantly, patients with primary MDD will be excluded from this trial. However, because symptoms of depression are likely to co-occur with anxiety, we also will assess depressive symptoms with the Beck Depression Inventory-II (BDI-II). The BDI-II is a widely used measure of depressive symptomatology, consisting of 21 items, each corresponding to a specific category of symptoms and attitudes. It has been shown to be both a reliable and valid measure of depression severity and has been used in many major interventional trials of cardiac patients. Item #9 (suicidality) of the BDI-II will be used to assess suicidal ideation and administered weekly along with the STAI.

Electronic-based questionnaires (e-questionnaires) will be used for all assessments, both anxiety and quality of life, except for interview-based assessments. These e-questionnaires will be delivered during participants' visits to Duke for pre- and post-intervention assessments. A Duke Psychiatry computer will be used and secured by Psychiatry Computer Support. The computer log-in will be performed and documented by study personnel; the computer will be used only for the survey purpose;

the study personnel will remain in the room with the participants while they have computer access; and study personnel will document log-off before leaving the room. The computer will be setup such that only necessary software will be installed on the computer, and access to other applications and network assets will be limited. The software necessary for assessments is Qualtrics, a Duke-approved survey platform.

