#### V. Post-treatment Assessments at 3-Months and at 9-Months (Six-month follow-up)

At the conclusion of the 3-month intervention (post-treatment), or at the time a participant may drop out of the study (or in the rare instance of requiring additional or different anxiolytic treatment outside of our protocol), patients will complete the same clinical, biomarker, and psychometric test battery that they completed at baseline. At the 6-month follow-up, we will assess anxiety, patients' exercise habits, any psychiatric treatment, psychopharmacologic medications, aerobic fitness using a 6-minute walk test, and cardiac status, including revascularization procedures and CHD events. This will be a naturalistic follow-up that we have used in previous trials,[157, 158] which will allow us to determine patients' anxiety status 6 months after the conclusion of study-related treatment, along with changes in health habits and measures of quality of life. Figure 2 presents an expanded view of the assessment schedule and design of the study. For clinical events, we carefully will document cardiac-related hospitalizations and

emergency room visits, revascularizations, and any deaths for up to 4 years post-treatment.

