symptom severity and, thus, study eligibility. This is a racially and socioeconomically diverse region, which will be reflected in our sample of anxious CHD patients. Patients from Duke, UNC, and outside hospitals will be considered for participation. Non-Duke patients will be provided with Duke's Notice of Privacy Practices.

**Inclusion criteria.** Men and women with documented CHD (i.e., a prior MI, coronary revascularization procedure, or >70% stenosis in at least one coronary artery) age  $\geq 40$  years will be selected for study. Patients also will have an anxiety symptom severity score of  $\geq 8$  on the HADS-A; a subgroup of patients will also have a DSM-5 diagnosis of an Anxiety Disorder. A modified GAD diagnosis will be used, wherein the GAD criteria include a minimum of 1 month of worry and at least 2 of the associated symptoms listed in DSM-V. Patients diagnosed with MDD may be included provided a) they have an anxiety diagnosis (e.g., generalized anxiety disorder, panic disorder, social anxiety disorder); b) their BDI-II total score is  $< 30$ ; c) their response to BDI-II item #9 (suicidality) is 0 or 1; and d) the psychiatric interview determines that the patient is at minimal suicide risk. For patients included that meet these criteria, suicidality will be assessed weekly throughout the duration of the trial as noted in Section 13 (Data and Safety Monitoring). We plan to actively recruit women and minorities, with at least 50% women and 25% minorities.

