**Exclusion criteria.** Medical exclusions will include an MI or coronary revascularization procedure (i.e., CABG or percutaneous coronary intervention) within the last 3 months, unstable angina, severe left ventricular dysfunction or decompensated heart failure (i.e., left ventricular ejection fraction  $< 30\%$  AND New York Heart Association functional classification of III or IV), unrevascularized left main coronary artery stenosis  $> 50\%$ , pacemaker dependence, resting BP  $> 200/120$  mm Hg, and conditions that would preclude randomization to either the drug (e.g., prolonged QT interval, known allergy to or intolerance of escitalopram) or exercise (e.g., musculoskeletal problems or abnormal cardiac response to exercise). Patients with a primary psychiatric diagnosis other than Anxiety Disorder will be excluded, including patients with MDD, PTSD, OCD, or any of the following DSM-5 diagnoses: 1) Dementia, delirium; 2) Schizophrenia, Schizoaffective, or other psychotic disorder; 3) Psychotic features including any delusions or hallucinations; or 4) Current alcohol or other substance abuse disorder. Further, patients with active suicidal ideation at screening and/or a history of a suicide attempt requiring inpatient admission will not be enrolled into the trial. To determine the risk for suicide, which would meet our exclusion criteria, any patient with a history of inpatient admission for MDD documented in the medical record will be excluded. Second, selection of BDI-II response choice 2 ("I would like to kill myself") or 3 ("I would kill myself if I had the chance") to BDI-II item 9 would be excluded. Similarly, patients who pose an acute suicide or homicide risk or who, during the course of the study, would likely require treatment with additional psychopharmacologic agents will not be enrolled. Patients will also be excluded if they are taking other medications that would preclude assignment to either drug or exercise conditions (e.g., clonidine, dicumarol, anticonvulsants, and MAO inhibitors) or are taking herbal supplements with purported mood effects (e.g., St. John's Wort, valerian, ginkgo). Patients already engaged in regular exercise (at least 30 minutes  $> 1x/week$ ) will not be enrolled. Finally, pregnant women will be excluded from participation.

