Patients will see [name] (who will be blinded to pill condition) at week 0 (baseline), week 1, week 2, week 4, week 8, and week 12 with phone consultations at weeks 3 and 6. Patients will be contacted weekly by telephone between regularly scheduled visits to take the STAI-State. [name] will make all medication adjustments based primarily upon STAI scores and safety/tolerability/side-effect assessments. Patients will be randomly assigned to receive escitalopram (5 mg/d) or placebo. Depending on symptoms, daily escitalopram (or placebo) doses will be titrated to 10 mg after week 2 and to 15 mg or placebo equivalent at week 3 if patients show no change or only minimal improvement. At week 4, if patients show no change or only minimal improvement, they will receive up to a maximum daily dose of 20 mg or placebo equivalent. The dose can be reduced in the event of side effects. [name] is an experienced clinical investigator in pharmacological RCTs and will serve as the treating psychiatrist for this trial. In all cases, the treating physician will use supportive measures to help manage medication side effects. In cases of severe side effects or patient discomfort, the physician may elect to decrease the medication dosage at any time or permit unscheduled visits during the study. At each medication dispensing visit, the patient will see the treating physician, who will prescribe the medication, and the study coordinator, who will order the medication, which will be signed off by the treating physician. The signed order will be released to and filled by the on-site investigational pharmacy. The pharmacy will dispense enough medication to last to the next expected dispensing visit plus a 5-day window. Patients will be instructed to use their previous bottle of medication before opening and using the newest provided bottle(s). The pharmacy will be responsible for medication storage and verifying expiration, maintaining the blind, storing codes in a sealed envelope accessible at emergencies, and for dispensing medication.

Patients and raters will be kept blinded to drug therapy assignments both during the treatment phase (3 months) and until the patient has completed the post-treatment assessments. [name], who will perform the ongoing medication monitoring and safety ratings, will be blinded until the completion of the trial. Limited use of sleep medications, but not other anxiolytic agents, will be permitted (see Human Subjects).

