
**13. Data and Safety Monitoring:** Study participants will be closely monitored for side effects, level of anxiety, and suicide risk. All patients will receive a weekly phone call to assess their state of anxiety using the STAI-State instrument. For patients who have a secondary diagnosis of MDD, BDI-II item #9 will be administered along with the 20-item STAI; patients who score  $>1$  on the item #9 of the BDI-II or who are judged to be at increased risk for suicidality will be evaluated by our study psychiatrist and referred for further treatment. For patients with a secondary diagnosis of MDD, suicidality will be assessed at each visit and by interim telephone contacts as needed. Subjects may experience no response to treatment or a worsening of symptoms; however, all subjects will be carefully monitored and withdrawn from the study if their symptoms worsen. If patients become suicidal, they will be evaluated by the treating psychiatrist

and appropriate referral or admission procedures will be initiated, such as to their referring physician or to the Duke Outpatient Affective Disorders Program, the Duke Psychology Clinic, or a local mental health center. Our study coordinator will contact the patient within 24 hours to make sure that he or she followed through with the referral. Furthermore, at the conclusion of the interventions, patients will be followed bimonthly via telephone and referred to their local physicians for further treatment, if necessary, or to the Outpatient Treatment Program at Duke University Medical Center or to the Duke Psychology Clinic.

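### Section 4.I gives BDI-II item #9 weekly with no subgroup named, while Section 13 provides it for patients with secondary MDD; the scope should be settled, preferably as all participants

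*Combined protocol and SAP*

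**What the plan says.** Section 4.I states the rule without a subgroup: "Item #9 (suicidality) of the BDI-II will be used to assess suicidal ideation and administered weekly along with the STAI". In that section the weekly STAI-State is completed by participants generally. The BDI-II is introduced because depressive symptoms tend to accompany anxiety, a reason that applies to the whole sample. The same section adds, with no instrument or timetable, "Suicidal potential also will be carefully assessed".

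Section 13 first gives every patient a weekly call for the STAI-State. It then says: "For patients who have a secondary diagnosis of MDD, BDI-II item #9 will be administered along with the 20-item STAI". A score above 1, or a judgement of increased risk, leads to evaluation by the study psychiatrist and referral.

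The inclusion criteria in Section 5 set conditions under which a patient with MDD may enter, and then say: "For patients included that meet these criteria, suicidality will be assessed weekly throughout the duration of the trial as noted in Section 13".

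Section 4.V repeats the baseline tests after treatment: "patients will complete the same clinical, biomarker, and psychometric test battery that they completed at baseline".

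**The concern.** A coordinator making the weekly call to a participant without MDD can find two answers in the protocol on whether to ask item #9. Section 13 is the safety section, so it is the one that staff are likely to follow.

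The participants affected include patients without MDD who are randomized to escitalopram. Section 10 acknowledges FDA alerts on SSRIs and worsening suicidal ideation and does not confine them to patients with MDD. Under the Section 13 reading, the score-based part of the trigger cannot operate for these participants between the baseline and 3-month assessments, because the item that produces the score is not asked. What is at stake is the consistency of safety monitoring. The trial's estimates, power and error rates are not involved.

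**Working it through.** No formula applies; the check is a comparison of the texts.

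1. **Section 4.I.** Item #9 is tied to the weekly STAI, and the weekly STAI is completed by participants without qualification. Read by itself, this gives item #9 every week to everyone.

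2. **Section 13.** One sentence gives the STAI call to all patients. The next opens with the secondary-MDD qualifier and adds item #9. If item #9 were meant for everyone, the qualifier would do no work. The natural reading is therefore a restriction, although no word expressly excludes other patients. Item #9 is weekly here because it accompanies the weekly STAI.

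3. **Section 5, inclusion criteria.** Weekly suicidality assessment is attached to the patients admitted under the MDD conditions, with a pointer to Section 13. This supports the restrictive reading of Section 13. It too stops short of excluding others.

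4. **Other text that might settle it.** The closing part of Section 13, on worsening depression and active ideation, mentions weekly assessments but names neither item #9 nor a population. Section 4.V refers to Figure 2 for the assessment schedule. That figure is not shown in our copy, so it may or may not resolve the point.

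5. **Consequence of each reading for a participant without MDD.** Under Section 4.I, item #9 is asked at each weekly call. Under the restrictive reading of Section 13, it is asked at none of them. On either reading the full BDI-II, which contains the item, would come round again with the 3-month battery, taking the BDI-II to be part of that battery.

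6. **What else covers these participants during treatment.**
   - *Pill arms:* scheduled contacts with the treating psychiatrist at "week 0 (baseline), week 1, week 2, week 4, week 8, and week 12 with phone consultations at weeks 3 and 6" (Section 9). Strictly between baseline and week 12 that is 4 visits (weeks 1, 2, 4, 8) + 2 calls (weeks 3, 6) = 6 contacts, which include safety and side-effect assessment. Of the 11 intervening weeks, 11 − 6 = 5 have no scheduled psychiatrist contact (weeks 5, 7, 9, 10, 11).
   - *Exercise arm (60 patients planned):* no equivalent psychiatrist schedule is stated.
   - *All arms:* weekly anxiety monitoring by a trained clinical psychologist (Section 10), general monitoring for suicide risk and the weekly call (Section 13), and advice to contact the team if symptoms worsen (Section 13).

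   For participants without MDD, none of these specifies a fixed suicidality question or a timetable for asking one.

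**The case against.** The strongest reply is that the two sections can both be obeyed. Asking item #9 of everyone breaches neither, and Section 13 nowhere limits the item to MDD in express terms. The missing schedule figure might also show the intended scope. Both points stand. They are why this is an ambiguity with a natural reading and not a proven contradiction.

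A second reply is that participants without MDD are a screened group. Section 5 excludes active suicidal ideation, a past attempt requiring admission, an inpatient admission for MDD, and acute suicide risk. Anyone choosing response 2 or 3 "to BDI-II item 9 would be excluded". Section 10 adds warnings in the consent form, counselling of all patients by the study psychiatrist, and immediate referral if such events develop. Weekly screening targeted at the higher-risk subgroup would be a legitimate choice. This also stands, and it lowers the priority. However, the exclusions act at entry, whereas the FDA alerts concern worsening on treatment. If targeting was intended, Section 4.I should say so.

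A reader might infer that participants without MDD go unmonitored for suicide risk. The documents do not support that, given the safeguards above. A reader might also multiply weekly calls by headcount and treat the total as the size of the problem. That would need an MDD share the protocol does not give, and it would count questions asked, not ideation missed.

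Finally, a reader might see a defect in the lack of an action specific to a score of exactly 1. Sections 5 and 13 consistently draw the line between 1 and 2. Section 13 also requires immediate evaluation of patients who report suicidal ideation, and a discretionary rule for a score of 1 could weaken that.

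**Conclusion.** The discrepancy in scope is real. Section 4.I names no subgroup for weekly item #9. Section 13, supported by Section 5, provides it for patients with secondary MDD, and no available text reconciles them. The conclusion rests on reading the Section 13 qualifier as a restriction and on Figure 2 not settling the matter.

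The practical effect, if staff follow Section 13 on that reading, is that participants without MDD, including those on escitalopram, have no item #9 check at the weekly calls. The general safeguards remain. The effect on harm cannot be quantified from the documents, and no efficacy analysis changes. This is a cheap improvement to patient safety, of low to moderate priority.

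**What to change.** Amend Section 13 so that item #9 is given to all participants at the existing weekly STAI call, in line with Section 4.I. State that the present trigger (a score above 1, or judged increased risk) applies to everyone. Keep the assessment of suicidality at each visit for patients with secondary MDD as an addition, and leave the requirement for immediate evaluation of reported ideation as it is. Check that Figure 2 agrees.

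Limiting Section 4.I to patients with MDD would also make the text consistent, but it would leave escitalopram patients without MDD with no item #9 check at the weekly calls.

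The cost is a wording amendment, one extra item on a call that every patient already receives, and some additional psychiatrist evaluations.
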